2.2 Secondary objective(s) and endpoint

2.2.1 Secondary objectives

1. Assess the safety and tolerability of ^{89}Zr -girentuximab administered by intravesical instillation.
2. Radiation protection management
3. Assess the degree of CAIX expression by immunohistochemistry of the tumor sample.

2.2.2 Endpoints of secondary objectives

1. The occurrence and the frequency of adverse events up to Day 30 after ^{89}Zr -girentuximab administration.
2. Radiation protection management:
 - ⇒ Radiation exposure of staff (extremities, lens and Whole body: μSv).
 - ⇒ Radiopharmaceutical management from intravesical instillation to elimination (surfacic contamination: counts/cm² or Bq/cm²).

3. The expression of CAIX will be assessed in TURBT or cystectomy tumor sample by immunohistochemistry (IHC).

3. PATIENT SELECTION

Each patient should meet all of the inclusion criteria and none of the non-inclusion criteria for this study. Under no circumstances can there be exceptions to this rule.

3.1 Population description

Patients with Non-Muscle-Invasive Bladder Cancer (NMIBC) requiring a radical cystectomy will be included in this study just before their surgery. Cancer treatment will not be delayed by study participation.

3.2 Inclusion criteria

Patients must meet all of the following inclusion criteria to be eligible for enrolment into the study:

1. Written informed consent obtained from the patient prior to performing any protocol-related procedures, including screening evaluations.
2. Willingness and ability to comply with scheduled visits, treatment plans, laboratory tests, and other study procedures.
3. Female or male, Age \geq 18 years at time of study entry.
4. PS: 0 or 1.
5. Clinical evidence of NMIBC based on cystoscopy and proven histologically of papillary tumors.
6. Histologically-confirmed pTa Grade 3 or pT1 Grade 3 bladder cancer patients relapsing without muscle invasion.
7. Negative sterile Urine cytobacteriological testing at baseline (T0).
8. Consent to use a contraception method for at least 42 days after administration of ^{89}Zr -girentuximab.
9. Patient has valid health insurance.
10. Negative serum pregnancy test in female patients of childbearing potential at screening.

3.3 Non-inclusion criteria

Patients should not enter the study if any of the following non-inclusion criteria are fulfilled:

1. Patient with urinary incontinence.
2. Known hypersensitivity to girentuximab.
3. Exposure to any experimental diagnostic or therapeutic drug within 30 days prior the date of planned administration of ^{89}Zr -girentuximab

4. Exposure to any radiopharmaceutical within 30 days prior to the administration of ⁸⁹Zr-girentuximab
5. Patients suffering from a bladder cancer at stage pT2, pT3 or pT4
6. Serious non-malignant disease that may interfere with the objectives of the study or with the safety or compliance of the patient; as judged by the investigator
7. Concomitant cancer in the past 5 years except cutaneous cancers (except melanoma) and in situ carcinoma
8. Prior chemotherapy, radiotherapy (other than short cycle of palliative radiotherapy), immunotherapy within 21 days of ⁸⁹Zr-girentuximab administration
9. TransUrethral Resection of Bladder Tumor (TURBT), BCG or Mitomycin C endovesical instillations within 10 days before ⁸⁹Zr-girentuximab
10. Patients with known HIV, HBV and HCV infections,
11. Pregnant or likely to be pregnant or nursing patient.
12. Mental impairment that may compromise the ability to give informed consent and comply with the requirements of the study
13. Persons deprived of their liberty, under a measure of safeguard of justice, under guardianship or placed under the authority of a guardian.

As patients are enrolled 10 days before the IMP administration, a confirmation of negative pregnancy test result from urine should be performed within 72 hours prior ⁸⁹Zr-girentuximab administration.

Validated methods of contraception for both men and women are pill, condom, intra-uterine device. Participation to another interventional therapeutic clinical trial is not authorized.

Procedures for withdrawal of incorrectly enrolled patients are presented in Section 4.4.

If a patient withdraws from participation in the study, then his or her enrolment code cannot be reused.

3.4 Withdrawal of patients from study

3.4.1 Permanent discontinuation of procedure

Patients may be discontinued from study in the following situations:

- Patient decision.
- Investigator decision.
- Patient did not undergo ⁸⁹Zr-TLX250 PET/CT imaging study procedure.

3.4.2 Withdrawal of consent

Patients are free to withdraw from the study at any time (study procedure and assessments) without prejudice to their further medical care.

In case of withdrawal of consent, the patient's study generated data may be used until withdrawal of consent date, unless the patient has objected.

3.5 Patients replacement

A patient who is included into the study, but then fulfils any one of the following, will be considered as drop-out:

- Has not received ^{89}Zr -TLX250 administration;
- Did not undergo ^{89}Zr -TLX250 PET/CT imaging after intra-vesical administration of study drug;
- Whose PET/CT images cannot be analysed due to technical failure;

Patients who dropped out of the study will be replaced. All patients who dropped-out after receiving intra-vesical ^{89}Zr -TLX250 will need to get all the examinations and blood draws as for the final study visit.

4. STUDY PROCEDURE ^{89}Zr -TLX250 PET/CT SCAN

4.1 Study drug ^{89}Zr -TLX250

4.1.1 Chemical Properties

^{89}Zr -TLX250, is a chimeric monoclonal antibody (INN name: Girentuximab) with specificity for the CAIX (carbonic anhydrase 9) antigen, radiolabelled with the positron emitting radio-metal zirconium-89.

The chemical formula, without the ^{89}Zr , is $\text{C}_{6460}\text{H}_{1006}\text{N}_{1718}\text{O}_{2018}\text{S}_{48}$ with a molecular mass of 146.5 kg/mol.

4.1.2 Pharmaceutical Properties

^{89}Zr -TLX250 is formulated as a solution for intravesical instillation in glass vials at the nominal dosage strength 37 MBq ($\pm 10\%$) for intravesical instillation use. The ^{89}Zr -TLX250 drug product is manufactured as “ready-to-use”. The composition of ^{89}Zr -TLX250 solution for intravesical instillation includes the active pharmaceutical ingredient in a buffered solution without other excipients.

A complete record of batch numbers and expiry dates of all study medication will be maintained in the trial master file (TMF).

4.1.3 Storage and Handling

The product is to be shipped and stored at room temperature (15°C to 30°C) inside the lead-shielded container provided and protected from light.

The product must be handled within a hospital environment only, by an accredited radiopharmacist and/or nuclear medicine physician according to international and local radiation protection guidelines.

4.1.4 Packaging and Labelling

^{89}Zr -TLX250 solution for intravesical instillation will be supplied in glass vials in appropriate packaging (lead-shielded containers bearing a radioactive warning symbol in accordance with radioactive pharmaceutical requirements). The labels of the packaging supplied by the sponsor will include the following information as a minimum:

- Name and address of sponsor
- Study number
- Name of study drug and formulation
- Dose strength
- Batch number

- Expiry date
- Storage instructions
- Radioactive warning symbol
- “For Clinical Trial Use only”.

All manufacturing, formulation and labelling will be done in accordance with applicable current GMP and local guidelines and laws.

Medication Numbering:

A system of medication numbering in accordance with all requirements of Good Manufacturing Practice (GMP) and any applicable regulatory requirement will be used for all study drugs. This will ensure that, for each patient, any dosing of study drug can be identified and traced back to the original bulk ware of the active ingredients.

Lists linking all numbering levels will be maintained by the institutions in charge of study drug packaging.

4.1.5 Drug Logistics and Accountability

4.1.5.1 Supply, Storage, Dispensation and Return

⁸⁹Zr-TLX250 solution for intravesical instillation will be manufactured, handled and stored in accordance with GMP. ⁸⁹Zr-TLX250 contains radioactive material and should only be handled by personnel trained in the use of radioactive isotopes with proper shielding and monitoring. Receipt and use of ⁸⁹Zr-TLX250 is limited to institutions holding an appropriate handling permit by their competent national or regional authority.

All required documentation, e.g. written approval from the independent ethics committee (IEC) and regulatory authority, as appropriate, needs to be provided before ordering for a site can take place. The dose order will be a direct order from the study site to manufacturer who shall arrange appropriate supply of IMP. Upon establishment of patient eligibility (see Section 3), the clinical site manager will order individualized doses of ⁸⁹Zr-TLX250 solution for intravesical instillation, via the manufacturer for direct delivery to the study site. A dose can be cancelled at any time however if the cancellation is less than 2 days prior to administration date then the site will need to inform manufacturer. ⁸⁹Zr-TLX250 for intravesical instillation will be provided by Telix International Pty Ltd and used unchanged from the original state. The treating investigator at the site will delegate ordering of ⁸⁹Zr-TLX250 solution for intravesical instillation to the clinical site manager, overseeing eligibility and planned treatment dates, for direct delivery to the site to the attention of the radiopharmacist.

The IMP will be shipped at room temperature (15°C to 30°C) inside an appropriately shielded container.

Upon receipt at site, ⁸⁹Zr-TLX250 solution for intravesical instillation will be kept in a secure, temperature-controlled, restricted-access location and in accordance with applicable regulatory

requirements at the radiopharmacy of the site. The IMP should be stored at ambient temperature (15°C to 30°C) without freezing, and should be used by the expiration date and time printed on the label.

⁸⁹Zr-TLX250 doses will be accompanied by an individual certificate of analysis for each batch. Upon verification of the correct radioactive dose, as specified by the study protocol, the radiopharmacist will hand over the investigational product in a syringe, kept in a lead-shielded container, to the nuclear medicine investigator, or a designated and suitably qualified deputy for administration. This syringe will be labelled by the radiopharmacist according to institutional standards.

Storage, handling and destruction must be performed according to local guidelines regarding radioactive waste management.

4.1.5.2 Drug Accountability

The radiopharmacist will confirm receipt of the study drug by e-mail and will use the study drug only within the scope of this clinical study and in accordance with this study protocol. He / she will keep a record of the dispensed study drug.

Receipt, distribution and return of the study drug must be properly documented on the forms provided by the sponsor giving the following information: study protocol number, sender, receiver, date, mode of transport, quantity, batch number, expiration date and retest date, if applicable.

The sponsor will monitor the drug accountability records at regular points during the study and will perform drug reconciliation at the end of the study.

4.2 Study procedure: ⁸⁹Zr-TLX250 PET/CT Imaging

All imaging sequences are done on an outpatient basis. The patient does not have to be fasting. There is no premedication or other treatment before and after the ⁸⁹Zr-TLX250 administration.

4.2.1 Dosage and Administration

This is sufficient to draw up the patient dose of 37 MBq of ⁸⁹Zr- TLX250, adjusted to 10 mg of girentuximab at the time of injection.

The study medication will be prepared as individual syringe in ICO radiopharmacy by a dedicated pharmacist within one hour of administration.

The investigator should check that the urine cytobacteriological testing is negative before intravesical instillation to ensure the absence of germs.

The ⁸⁹Zr-Girentuximab solution (about 10 ml) will be administered into the emptied bladder through a urethral catheter using natural urinary tract (see intravesical instillation procedure in appendix 7).

The syringe will be washed with 30 ml of saline solution which will be also injected into the bladder. The urethral catheter should be removed.

Patients will be asked to turn over repeatedly to ensure equal distribution of ⁸⁹Zr-Girentuximab in the bladder.

The ⁸⁹Zr-Girentuximab should be maintained in the bladder for no more than 1.5 hours: duration of ⁸⁹Zr-Girentuximab administration.

Then, the patient will be asked to drink water and urinate to rinse the bladder, the patient will drink water again and the first PET/CT imaging centered on the bladder will be performed about 2 hours after instillation.

The urethral catheter and the urine activity will be measured.

A whole body imaging should be performed 2 hours after ⁸⁹Zr-Girentuximab administration (4 hours after instillation) (see intravesical instillation procedure in appendix 7).

The investigator or his/her designee will administer the study drug to the subjects, exercising accepted medical practices. Under no circumstances will the investigator allow study drugs to be used otherwise than as directed by this clinical study protocol. Study drug administration will be done under direct medical supervision.

4.2.2 ⁸⁹Zr-TLX250 PET/CT Imaging

Imaging sessions are necessary to check the safety of intravesical application of ⁸⁹Zr-TLX250 pharmaceuticals. Two aspects will be studied:

- **T0:** At the end of ⁸⁹Zr-TLX250 administration: 2 hours after intravesical instillation, a first imaging session centred on the **bladder** will be performed (with full bladder) and will allow to evaluate the possibility to identify the ⁸⁹Zr girentuximab uptake surface and to measure tumor and normal bladder wall surface. Spatial distribution of PET/CT images will cover the lone bladder. PET acquisition duration will be adjusted to allow a sufficient count statistics for a good quality of activity measurements in main organs.
- **T0 + 2 hours:** a **whole body scan** will be performed (with empty bladder), from the skull base to the mid-thigh, to ensure that no residue ⁸⁹Zr-TLX250 pharmaceutical occurred outside the bladder and spread in the rest of the body. During the whole body scan, the specific step including the bladder will be designed.
- **T0 + 20 hours (day 1):** a new imaging session centred on the **bladder** will be performed (same protocol as first session) in order to quantify the remaining activity and calculate the decay of the later. The aim is to check that there is no residual radiopharmaceutical outside the bladder through the urethra.

On day 1, a blood sample will be drawn in order to check the absence of activity from residual ⁸⁹Zr-TLX250 in blood.

- **T0 + 44 hours (day 2):**
 - ⇒ If blood radioactivity testing on day 1 is **negative**, a **bladder scan** should be performed on day 2 (T0 + 44 hours).
 - ⇒ If blood radioactivity testing on day 1 is **positive**, a **Whole body scan** should be performed on day 2 (T0 + 44 hours). This scan will permit to localise the uptake of the residual pharmaceutical.

In total, 4 imaging sessions will be performed, including a whole body scan and in case of residual activity in the day 1 blood sample, a second whole body scan will replace the bladder centred scan.

PET studies will be performed with a PET/CT hybrid system. A CT acquisition will be coupled to a PET acquisition for attenuation correction and anatomical tracking.

Low-dose CT acquisition parameters will be those usually used namely:

- Field: several fields of view allowing visualization of the bladder and whole body.
- Number: four acquisition times:
- Time 0: 2 hours after instillation:
 - Full bladder imaging: one step centred on the bladder after CT acquisition of the step.
- ⇒ Time 1: 4 hours after instillation:
 - Whole body scan after scout view and low dose CT acquisition, to cover area from skull base to mid-thigh. The step on the bladder is included into this whole body scan.
- ⇒ Time 3: 20 hours after instillation (day 1):
 - One step acquisition centred on bladder with low dose CT
- ⇒ Time 4: 44 hours after instillation (day2): depending on the day 1 blood sample results (in terms of activity in Bq/ml),
 - In case of negative result (no activity i.e. background): One step acquisition centred on bladder with low dose CT.
 - In case of positive result (activity > 2.5 times background): Whole body scan after scout view and low dose CT acquisition, to cover area from skull base to mid-thigh. The step on the bladder is included into this whole body scan.

Comment: These times should be adapted according to practical arrangement of intravesical instillation.

- Standard whole body scan = 100 kV, 5 mm, Acq 16x1,2 mm, pitch 1, CAREDOSE4D, CAREkV
- One step high accuracy CT: 120 kV, 4mm slices every 4 mm and 0.85 pitch CAREDOSE4D, CAREkV
One step low dose CT: 100 kV, 5mm, Acq 16x1.2mm, pitch, CAREDOSE4D, CAREkV

The CT acquisitions centred on the bladder will visualize a field of about 20 cm and consequently will deliver a low dose corresponding to a DLP of around 130mGy.cm and an effective dose of around 3 mGy.

The whole body CT acquisitions, from skull base to mid-thigh, will visualize a field depending of the height of the patient. For standard 170cm height, this will deliver a low dose corresponding to a DLP of around 350mGy.cm and an effective dose of around 5 mGy.

The total effective dose resulting from successive CT acquisitions for attenuation correction can be estimated from 14 to 16 mSv. This dose should be compared to a diagnostic CT acquisition dose to thorax and abdomen, which is about 15 to 16 mSv.

4.2.3 Imaging Analysis

4.2.3.1 Qualitative ^{89}Zr -TLX250 Tumor Targeting

^{89}Zr -TLX250 tumor uptake will qualitatively be assessed, considering whether or not ^{89}Zr -TLX250 binding the target bladder lesion.

We would like to show that ^{89}Zr activity remain in the bladder and that no systemic uptake and reflux into the ureters is observed as described in a previous clinical pilot study with intravesical instillation of ^{213}Bi - anti- EGFR MAb (6).

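### The planned scans can show that no activity is retained in the ureters or kidneys about 4 h after instillation; they cannot show the absence of reflux that section 4.2.3.1 sets out to show

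*Combined protocol and SAP*

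**What the plan says.** Section 4.2.3.1 states, as something the team would like to show, that activity remains in the bladder and that "no systemic uptake and reflux into the ureters is observed". The benchmark is the earlier bismuth-213 pilot study of intravesical instillation.

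Section 4.2.1 gives the order of events. The tracer "should be maintained in the bladder for no more than 1.5 hours". After that "the patient will be asked to drink water and urinate to rinse the bladder", the patient drinks again, and the "first PET/CT imaging centered on the bladder will be performed about 2 hours after instillation".

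Section 4.2.2 and the schedule of assessments give the coverage:

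- **T0 (about 2 h after instillation):** full bladder. "Spatial distribution of PET/CT images will cover the lone bladder".
- **T0 + 2 h (4 h after instillation):** whole body from skull base to mid-thigh, empty bladder.
- **Day 1:** bladder-centred, by the same method as T0.
- **Day 2:** bladder-centred, replaced by a whole-body scan only if the day 1 blood sample is positive.

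Section 4.2.2 also gives a second description of the bladder-centred coverage: "The CT acquisitions centred on the bladder will visualize a field of about 20 cm".

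Section 2.1.2 lists whole-body biodistribution, assessed visually and quantitatively, among the primary endpoints. It does not name reflux. Neither section 2.1.2 nor section 4.2.3 defines a ureter or kidney region or a rule for reading one.

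**The concern.** Instilled tracer could reflux while it is in the bladder or while it is being voided. The schedule takes no image in the first period, and by the time the upper tract is imaged the patient has drunk, voided, drunk again and emptied the bladder once more. Refluxed tracer that drained back in the meantime would leave nothing to see.

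The risk lies in interpretation. If all six whole-body scans are clean, section 4.2.3.1 invites the sentence that no reflux occurred, when the data show only that none was retained. The trial is meant to prepare for a therapeutic product given by the same route, and sections 1.3 and 1.4.4 already rely on the pilot's finding of confinement to the bladder when they argue that no toxicity is expected. A reader of this trial's report could use a no-reflux statement in the same way.

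**Working it through.** **Inputs.** Hold of at most 1.5 h and first scan at about 2 h (section 4.2.1); whole-body scan at T0 + 2 h, stated as 4 h after instillation (schedule of assessments, section 4.2.1); bladder-centred field of about 20 cm (section 4.2.2); zirconium-89 half-life of about 3.3 days (section 1.2.3.1); 6 patients (section 8.1).

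**1. Timing.** The plan's own figure reproduces: T0 at 2 h, plus 2 h, is 4 h.

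- End of a full-length hold to the T0 scan: 2 − 1.5 = 0.5 h, with a void in between.
- End of a full-length hold to the whole-body scan: 4 − 1.5 = 2.5 h. A shorter hold makes the gap longer.
- If the end of administration is read as the end of the 1.5 h hold, the whole-body scan falls at 1.5 + 2 = 3.5 h, a gap of 2.0 h.
- Section 1.3 describes bladder lavage two hours after instillation. If the bladder is emptied only then, the gap is 4 − 2 = 2 h. This should be reconciled with section 4.2.1. The T0 endpoint in section 2.1.2 is defined after rinsing, so on this reading too T0 follows the hold.

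On every reading no scan falls within the hold, and the full upper tract is first imaged 2 to 2.5 h or more after it.

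**2. Decay.** Half-life 3.3 × 24 = 79.2 h. Fraction remaining = 0.5^(t/79.2): 98.3% at 2 h and 96.6% at 4 h. Decay would not hide refluxed tracer at 4 h; drainage and washout could.

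**3. Field at T0.** A 20 cm field centred on the bladder reaches 20/2 = 10 cm above its centre. The documents give no bladder height. Assuming 6 to 14 cm, the field extends 10 − 3 = 7 cm down to 10 − 7 = 3 cm above the dome. Some distal ureter may therefore be visible at T0. This does not match the bladder-only wording in the same section.

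**4. Number of informative images.** Each patient has one guaranteed image of the kidneys and full ureters. The second whole-body scan depends on blood activity, which is not a test for activity in the urinary tract.

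**5. Precision of 0 of 6.** With perfect detection, the one-sided 95% upper limit is 1 − 0.05^(1/6) = 39.3%. The upper limit of the two-sided exact 95% interval is 1 − 0.025^(1/6) = 45.9%. These follow from n = 6 and have nothing to do with scan timing.

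Timing would enter through the share *s* of patients with reflux during the hold in whom it is still visible at 4 h: solving (1 − p·s)^6 = 0.05 gives p = 0.393/*s*. The documents give no value for *s*. If it were 75% or 50% (assumed), the one-sided limit on reflux during the hold would be about 52% or 79%.

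**The case against.** The strongest reply is that section 4.2.3.1 expresses a hope about what will be observed. Reflux is not an objective or a listed endpoint and has no decision rule. Section 4.2.2 already describes the whole-body scan as a check for residue outside the bladder, close to the narrower claim. The study is exploratory, with descriptive summaries only. This stands and limits the weight of the point. It does not remove it, because 4.2.3.1 is the imaging analysis section and so guides what is reported.

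Four stronger readings are tempting, and the documents do not support them:

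- **Nothing above the bladder is seen before 4 h.** The 20 cm field may take in some distal ureter at T0.
- **The 4 h scan says nothing about reflux.** It covers the whole urinary tract with about 97% of the physical activity left, so it could show retained refluxed tracer. The documents give no upper-tract clearance data, so how much it would miss is unknown.
- **The day 1 bladder scan is given an aim it cannot meet.** Its text reads "The aim is to check that there is no residual radiopharmaceutical outside the bladder through the urethra". As written, this concerns the urethra, part of which a bladder-centred field may cover, and not the upper tract.
- **The result would mislead about the astatine-211 product because its hold would be the same.** No hold time for that product is stated.

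The plan also cannot be called weaker than its benchmark: section 1.4.4 gives no imaging time for the pilot's no-reflux finding. Finally, the detailed procedure is in Appendix 7, which is not part of the text available here, and section 4.2.2 allows scan times to be adapted. Either could change the exact gaps.

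**Conclusion.** The point holds in a limited form. None of the hold, at most 1.5 h, is imaged. The kidneys and full ureters are first imaged about 4 h after instillation, after hydration and voiding and with an empty bladder. A negative scan supports absence of retained ureteral or renal activity at about 4 h and leaves transient reflux during the hold or void unexcluded. A no-reflux conclusion would be unsupported for that period, which is different from being shown wrong.

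This rests on the order of events in section 4.2.1 and on the scan times as written. The statement about distal ureter at T0 rests on an assumed bladder height.

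**What to change.** 1. In section 4.2.3.1, replace the reflux aim with: 'no residual activity in kidneys or ureters about 4 h after instillation'. Add that reflux while the tracer is held in the bladder is not assessed.
2. On the whole-body scans already planned, score kidneys and ureters as named regions: activity present, yes or no, and Bq/mL. Report the T0 + 2 h count out of 6 with an exact binomial interval.
3. In section 4.2.2, reconcile the bladder-only description of the T0 images with the field of about 20 cm, so that it is clear whether distal ureter is in view and will be read.

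This needs wording and region placement on existing images, with no added scan, visit or patient. Widening the T0 field would not be a substitute, since the bladder has already been voided by then. The cost is a narrower claim.
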